8. CONFIDENTIALITY AND STORAGE AND ARCHIVING OF STUDY DOCUMENTS

All documents and electronic files will be kept in a secure area with access given to authorised personnel only. Data used for reporting purposes will be de-identified and only group data will be

used in any publications arising from this trial. Documents and electronic files will be kept indefinitely following the completion of the trial.

9. FUNDING

The Garvan Institute of Medical Research has received a grant from the Paul Ramsay Foundation for the conduct of the study on the St Vincent's Hospital Research Campus (St Vincent's Hospital Sydney, the St Vincent's Prostate Cancer Centre and the Garvan Institute of Medical Research).

The Wesley Research Institute will fund the conduct of the trial and the recruitment of participants at the Wesley Hospital, Brisbane.

10. OTHER STUDY DOCUMENTS

Appendix A: Magnifi Trial: Eligibility Check List Version 1.1 1st Oct 2015

Appendix B: St Vincent's Hospital HREC Serious Adverse Event Reporting Form June 2015

Appendix C: Protocol Infusion "Combidex" Nano MRL Version 1.0 29th Sept 2015

Appendix D: Repeat Combidex (ferumaxtran-10) correspondence from [name], 15th March 2018.

| | |
|------------------------|----------------|
| Office use only | Initial: _____ |
| PT ID: _____ | Date: _____ |

ELIGIBILITY CHECK LIST MAGNIFI TRIAL

This form is to assess the eligibility of the participant for the Magnifi Trial

| | | |
|----------------------------|-------------|------|
| Patient Details (or Label) | | |
| Surname: | Given Name: | MRN: |
| DOB: | Address: | |
| Telephone: | | |

| INCLUSION CRITERIA | | EXCLUSION CRITERIA | |
|--|--|--|--|
| Male, aged 18 years or over |  Yes  No | Past history any other type of cancer (except skin cancer). |  Yes  No |
| Confirmed adenocarcinoma of prostate and at least clinical stage T3A and/or Gleason sum $\geq 4+3=7$, or preoperative PSA ≥ 15 ng/ml and planned radical prostatectomy |  Yes  No | Previous treatment for prostate cancer (surgery, radiotherapy, chemotherapy, hormone androgen deprivation therapy) |  Yes  No |
| Suspected lymph node involvement pre- radical prostatectomy based on Briganti nomogram $\geq 10\%$. |  Yes  No | Proven bony metastatic disease, visceral metastases or lymph node metastases above the level of the aortic bifurcation |  Yes  No |
| Suitable for radical prostatectomy and pelvic lymph node dissection, as per institutional guidelines and not yet treated pre-prostatectomy |  Yes  No | Previous surgery in pelvis (e.g. bilateral hip replacement) that limit the extent of pelvic lymph node dissection |  Yes  No |
| Subject is able to understand and willing to sign the participant information statement and consent form |  Yes  No | Patients who refuse radical prostatectomy or pelvic lymph node dissection |  Yes  No |
| Subject is expected to remain available for 24 months of clinic visits |  Yes  No | Patients who refuse to join the trial or are unable to consent |  Yes  No |
| | | Patients not being considered for further therapy |  Yes  No |
| | | Patient has absolute contra- indications to undergoing MRI scanning |  Yes  No |
| | | Patients who cannot lie still for at least 60 - 75 minutes or comply with imaging |  Yes  No |

| INCLUSION CRITERIA | | EXCLUSION CRITERIA | |
|--------------------|--|--|--|
| | | Subject has medical conditions that would limit study participation (per physician discretion) |  Yes  No |
| | | Subject is enrolled in one or more concurrent studies that would confound the study results of this study as determined by the study investigators |  Yes  No |
| | | Subject has a limited life expectancy that would not allow completion of the 24 month visits |  Yes  No |

I have assessed _____ for participation in the Magnifi Trial.

Tick one box only

- He has met ALL the inclusion criteria (responses must all be "Yes") and none of the exclusion criteria (responses must all be "No"). He is eligible to participate in the Magnifi Trial.
- He has NOT met ALL the inclusion criteria (responses must all be "Yes"). He is ineligible to participate in the Magnifi Trial

Signature of Assessor: _____

Name of Assessor: _____

Date of Assessment: _____

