| | 
 • Previous surgery in pelvis (e.g. bilateral hip replacement) that limit the extent of pelvic lymph node dissection • Patients who refuse radical prostatectomy or pelvic lymph node dissection • Patients who refuse to join the trial or are unable to consent • Patients not being considered for further therapy • Patient has absolute contra-indications to undergoing MRI scanning • Patients who cannot lie still for at least 60 to 75 minutes or comply with imaging • Subject has medical conditions that would limit study participation (per physician discretion) • Subject is enrolled in one or more concurrent studies that would confound the study results of this study as determined by the study investigators • Subject has a limited life expectancy that would not allow completion of the 24 month visits |
| STUDY PROCEDURES St Vincent's Hospital, Sydney | 
 1. Men diagnosed with prostate cancer are referred to a participating urologist for a radical prostatectomy 2. The patients are consented to the study by the urologist following fulfilment of the selection criteria 3. The patient is referred to the Department of Nuclear Medicine, St Vincent's Hospital, Sydney 4. The 68Ga-PSMA PET Scan is performed at the Department of Nuclear Medicine, St Vincent's Hospital, Sydney 5. On the return visit, "Combidex" is administered to the patient and the patient is referred to Medscan Barangaroo for a MRI scan 6. Radiologist and Urologist annotate suspect lymph nodes using the Pelvic Lymph Node Diagnostic Template and assign index of suspicion to each area 7. Patient undergoes radical prostatectomy including the removal of lymph nodes 7-10 days following Combidex nano-MRL 8. The prostate and the lymph nodes are sent to histology for reporting 9. Analysis: 
 a. Histology Vs Nano-MRL b. Histology Vs Ga68 PSMA PET c. Histology Vs Nano-MRL Vs Ga68 PSMA PET 10. Repeat Ga68 PSMA and Nano-MRL if not concordant with Histology within 6-8 weeks of surgery 11. Follow up Visits: The participant will have clinical follow up reviews as part of their care at 6 weeks, 2 months, 6 months, 12 months and 24 months 12. Participant will complete the Expanded Prostate Cancer Index Composite (EPIC) survey at baseline (prior to surgery), 6 weeks, 3 months, 6 months, 1 years and then yearly for a minimum of 5 years). |

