4.2. EXCLUSION CRITERIA

[figure not shown]
Patients who meet any of the following exclusion criteria are not eligible to participate in the study.

- Previous treatment for prostate cancer (surgery, radiotherapy, chemotherapy, hormone androgen deprivation therapy)
- Secondary malignancy except skin cancer
- Proven metastatic disease
- Patients who refuse radical prostatectomy or pelvic lymph node dissection
- Patients who refuse to join the trial or are unable to consent
- Patients not being considered for further therapy
- Patient with previous pelvic surgery (e.g. bilateral hip replacement) that will limit the eLND
- Contra-indication to MRI scanning, IV iron infusion, allergy to dextran or other injectable contrast media used in this trial
- Patients who cannot lie still for at least 60 - 75 minutes or comply with imaging
- Unequivocal evidence of disease outside the pelvis on conventional imaging
- Subject has medical conditions that would limit study participation (per physician discretion)
- Subject is enrolled in one or more concurrent studies that would confound the study results of this study as determined by the study investigators
- Subject has a limited life expectancy that would not allow completion of 24 month visits

- Subject meets the exclusion criteria required by local law

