5. STUDY OUTLINE

5.1. STUDY FLOW CHART

5.2. INVESTIGATION PLAN

1. Screening Procedures

Participants will be screened when they attend their first urology consultation for a radical prostatectomy following the diagnosis of prostate cancer. The participant will be intermediate and high-risk cancer patients with a $\geq 10\%$ probability on LN where LND would currently be performed as part of the treatment protocol (guided by the updated Briganti nomogram) [34]. All patients will have a clinical work-up in line with the current international guidelines for the treatment of high-risk prostate cancer including a pelvic MRI and routine bone scan. They will be assessed against the inclusion and exclusion criteria. Should they be deemed eligible for the trial, they will be provided with details of the trial and will be asked to participate by providing written consent.

2. Imaging

Participants who have consented to participate will then be referred to the St Vincent's Nuclear Medicine Department will have the following imaging services prior to surgery:

- 68Ga-PSMA PET scan
- Diagnostic CT (part of the 68Ga-PSMA PET scan)

In the event that a participant had a clinically indicated 68Ga-PSMA PET scan within 3 weeks at St Vincent's Hospital, the participant will not be required to have another scan. If the 68Ga-PSMA PET scan was performed elsewhere, the participant will be required to have one performed at St Vincent's Hospital for consistent reporting. The 68Ga-PSMA PET scan will be double assessed by two experienced readers at St Vincent's Hospital, Sydney and the Wesley Hospital.

At the return visit and prior to the surgery, Combidex, the imaging agent, will be administered to the patient at St Vincent's Hospital, Sydney. Combidex will be administered by a trained member of staff. Combidex will be administered by slow infusion over approximately 30 minutes following dilution in 100mls of normal saline. This method of administration minimises adverse events and allows the management of adverse should they occur by the halting the infusion. The protocol for Combidex Nano MRL infusion is found appendix C.

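### The Appendix A eligibility checklist and the synopsis leave out section 4.2's exclusions for IV-iron contra-indication and for dextran or contrast allergy, so the signed form can pass a man whom section 4.2 excludes

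*Protocol*

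**What the plan says.** Section 4.2 sets the rule: "Patients who meet any of the following exclusion criteria are not eligible to participate in the study". One of its items is "Contra-indication to MRI scanning, IV iron infusion, allergy to dextran or other injectable contrast media used in this trial".

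The synopsis has its own exclusion list. Its corresponding item is "Patient has absolute contra-indications to undergoing MRI scanning", with nothing on iron, dextran or contrast media there or elsewhere in that list.

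The Appendix A checklist carries the same reduced item, "Patient has absolute contra- indications to undergoing MRI scanning". The form gives its purpose as "This form is to assess the eligibility of the participant for the Magnifi Trial". When all inclusion answers are Yes and all exclusion answers are No, the assessor ticks a declaration that ends "He is eligible to participate in the Magnifi Trial", then signs and dates it.

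On screening, section 5.2 says of the men "They will be assessed against the inclusion and exclusion criteria". Sections 5.4 and 5.6 say much the same. None of the three states which of the protocol's lists is meant.

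**The concern.** The three lists disagree on the exclusion most specific to the investigational agent. Appendix C describes Combidex as iron-dextran nanoparticles given intravenously, and it is part of the imaging planned for every participant. Men whose imaging is positive but whose histology is negative are to have a second Nano MRL under section 5.2. Section 5.3 itself warns of hypersensitivity, anaphylaxis and cardiac compromise with intravenous iron or dextran products.

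What is at stake is participant safety and the validity of enrolment. A form completed exactly as printed can return a verdict of eligible for a man whom section 4.2 rules out, and he would then be booked for the infusion that the exclusion is meant to keep from him.

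**Working it through.** No formula applies, so the check compares the texts.

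**Step 1: the conditions on the section 4.2 line.** Read in the ordinary way, the line covers four conditions.

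| Condition | Section 4.2 | Synopsis | Appendix A |
|---|---|---|---|
| Contra-indication to MRI | Yes | Only if absolute | Only if absolute |
| Contra-indication to IV iron infusion | Yes | No | No |
| Allergy to dextran | Yes | No | No |
| Allergy to other injectable contrast media used in the trial | Yes | No | No |

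One of four is carried over, in narrower form; 4 − 1 = 3 are missing from both other lists.

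**Step 2: is the exclusion placed elsewhere in those lists?** Counting every exclusion item, section 4.2 has 14, the synopsis 12 and Appendix A 12. Items naming iron, dextran or contrast media number 1 of 14, 0 of 12 and 0 of 12. The condition has not been moved to another line.

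**Step 3: what the form does with such a man.** Take a man with a known dextran allergy and no other exclusion. Every specific exclusion line on the checklist is truthfully answered No. The only line that could stop him is the one on medical conditions limiting participation, which is left to the physician's discretion and does not mention iron, dextran or contrast. If it is answered No, the form declares him eligible. Section 4.2 does not.

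**Step 4: does any later step catch him?**

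- Sections 5.2, 5.4 and 5.6 each require assessment against the criteria (three instructions). None names Appendix A, and none says that section 4.2 prevails over the shorter lists. Section 5.6 names only Form A, for demographic and clinical information.
- The referral information listed in section 5.4 covers imaging, demographics, PSA with stage and grade, and prior therapies. Allergy history is not listed.
- Appendix C has 5 preparation and 8 administration steps, 5 + 8 = 13. None asks about allergy.
- The hospital contrast allergy protocol is reproduced only from its section 5, on treating reactions. Its earlier sections are not shown and cannot be judged.
- The section 5.3 precautions (resuscitation kit at the bedside, anaesthetist and intensive care on standby) deal with a reaction once it happens. They do not screen for the risk.

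**The case against.** The strongest reply is that section 4.2 governs, is correct, and is what the urologist is told to apply. No body section directs anyone to use Appendix A, so its practical role is partly inferred. The assessor also attests that the man meets none of the exclusion criteria, which could be read as reaching back to section 4.2. A competent clinician who knows of a dextran allergy should answer Yes on the medical-conditions line, given that the study infuses an iron-dextran agent. Before the infusion there must be a valid prescription and a second practitioner's check of the dose, and a radiologist starts it. The discrepancy touches no endpoint, power calculation or analysis, so one could call it a document-control matter.

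Part of this stands. There is a route to exclusion on the form; what is missing is the specific prompt, and a wrong sign-off requires that the allergy is not elicited or is judged not to matter.

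The rest does not dispose of the point. The form states its own purpose as assessing eligibility, and the attestation is tied in brackets to the printed answers. Section 4.2 carries the same discretionary line alongside the specific exclusion, so that line was not meant to replace it; relying on it turns a mandatory exclusion into a matter of judgement. The prescription, the dose check and the radiologist's attendance are further clinical contacts, but none is described as an allergy screen.

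**Conclusion.** The concern holds. Three of the four conditions on the section 4.2 line are absent from both the synopsis and the checklist, and the fourth is narrowed. The checklist can therefore certify a man whom section 4.2 excludes, for an agent whose class risk the protocol itself states. It should be fixed on safety grounds.

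The limits are these. A wrong sign-off is possible, not certain, and the number of men affected cannot be derived from the protocol. The conclusion takes the checklist at its stated purpose and makes no claim about Form A or the unseen sections of the hospital allergy protocol. The checklist is Version 1.1 of October 2015 and the protocol is version 2.4 of January 2019, so the form may simply not have been updated; that is an inference. There is no effect on sample size, power or analysis.

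**What to change.** Copy the section 4.2 exclusion on IV iron, dextran and contrast media word for word into the synopsis and into Appendix A, giving it its own Yes/No box on the form, and reissue the checklist under a new version number. Section 4.2 stays as it is.

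The MRI wording should be brought into line in the same edit, since the qualifier *absolute* is not in section 4.2. It would also be sensible to compare the remaining items while the form is open: the metastatic-disease wording differs, and the items on disease outside the pelvis and on local law are in section 4.2 only.

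The cost is a minor amendment and a reissued form. No man eligible under section 4.2 is lost, because the added line only repeats an exclusion already in force.

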Appendix B: St Vincent's Hospital HREC Serious Adverse Event Reporting Form June 2015

| |
|---|
| 
St Vincent's Hospital Sydney Human Research Ethics Committee (HREC)
 
SERIOUS ADVERSE EVENT (SAE) and/or
 
SUSPECTED UNEXPECTED SERIOUS ADVERSE REACTION (SUSAR) REPORT
 |
|---|

Instructions

1. Complete this form electronically before printing (hand written forms will not be accepted)
2. Please enter only one event per form
3. SAEs and SUSARs must be reported to the HREC:
 - a) For investigator initiated studies, within **24 hours** of the researchers becoming aware of the event
 - b) For all other studies, within **72 hours** of the researchers becoming aware of the event.

Adverse event reporting for clinical trials involving therapeutic products, must meet the requirements of the National Health and Medical Research Council, Australian Health Ethics Committee (AHEC) Position Statement "Monitoring and reporting of safety for clinical trials involving therapeutic products" (May 2009), which can be found at:

www.nhmrc.gov.au/guidelines-publications/e112

Initial electronic submission will meet reporting timelines however this must be followed by the submission of a full report in hard copy.

4. For multi-centre studies, the Principal Investigator is responsible for reporting SAEs and SUSARs at their site directly to the Lead HREC. A copy of this report, once acknowledged by the Lead HREC, should be provided to the site Research Governance Officer and the Coordinating Investigator.
5. All other safety reports, such as line listings, should be submitted directly to the Lead HREC by the Coordinating Investigator
6. Please submit both a **hard copy** and an **electronic copy** of the completed report:

| | |
|--|--|
| 
Electronic copy to be sent to: [contact]
 
The hard copy must have an original signature from the site Principal Investigator.
 | 
Original to be sent to: Research Office [name] St Vincent's Hospital [name]
 |
| 
A copy of the signed form should be retained by the Investigator
 | |

| Research Project Details | |
|---|--|
| SVH File Number (xx/xxx) | |
| HREC Reference Number (eg. HREC/xx/SVH/xxx) | |
| Full Study Title | |
| Coordinating Principal Investigator (for single centre studies, this is synonymous with Principal Investigator) | |
| Principal Investigator at site where participant is enrolled (If multi-site study) | |
| SAE/SUSAR* Event Details | |
| *Note SUSARS submitted on this form must have occurred at a site under SVH HREC approval | |
| Participant study identification number/code | |
| SITE NAME where participant was consented | |
| Date event occurred | |

| | |
|---|---|
| Date event resolved | OR Event ongoing  |
| Type of report The submission of supporting documentation is required for all INITIAL events: ie: For Investigator initiated studies, submit a copy of source documentation ie. relevant (de-identified) section from relevant medical records For Commercially sponsored or collaborative group studies, submit a copy of the sponsor's completed adverse event report form | Initial  Follow-up  Final  If this is an initial event, please ensure you submitted the appropriate supporting documentation. Is this information provided with this report: Yes  No  If no, please note that hardcopy SAE/SUSAR forms received without supporting documentation will be returned. If this is a follow-up and/or final report, please provide the date of initial report: Initial report date |
| Description of Event (Please provide a brief clinical description) | |
| Investigator's opinion of relationship of the adverse event to the study drug, device, intervention, procedure. | Unrelated  (clearly not related) Possibly  (may be related) Probably  (most likely related) Definitely  (clearly related) |
| Has this event been reported to the sponsor? | Yes  No  N/A  If NO, please provide detail why not: |
| Does the Investigator believe that this event may affect the ongoing ethical conduct of the study or the safety of the participants or their willingness to continue participation? | Yes  No  Please comment: |
| Does the event necessitate amendments to: The Study Protocol The Participant Information Sheet and Consent Form Other | Yes  No  Yes  No  N/A  Yes  No  If YES, please confirm when these amendments will be submitted for HREC review: |

Appendix C: Protocol Infusion “Combidex” Nano MRL Version 1.0 29th Sept 2015

Protocol Infusion “Combidex” Nano MRL Version 1.0 29th Sept 2015

To perform a MRI NANO scan, infusion of NANO contrast fluid (Combidex) is required (Iron-Dextran nanoparticles 20mg/ml). The contrast fluid should be administered 24 to 36 hours before the MRI scan, by intravenous infusion that will take at least 30 minutes for administration. In this protocol we describe how the NANO contrast fluid should be prepared and administered.

Equipment Required:

| Material | Quantity |
|--|----------------------------|
| Drawing up equipment (10ml syringe, 18g needles x 2) | 1x |
| Sodium Chloride 0.9% | 2x 100ml |
| Cannulation equipment | 1x |
| Intravenous Giving Set | 1x |
| Intravenous Infusion Pomp | 1x |
| Iron-Dextran nanoparticles 200mg Iron = 10ml (20mg/ml) (NANO contrast fluid “Combidex”) | Based on total body weight |
| Filter 0.22 µm | 1x |
| Alcohol Swabs | 1x |

Dose table. The dose of Iron-Dextran Nanoparticles 20mg/ml is based on body weight = 0.13 ml per kg.

| Kg | Dose | Kg | Dose | Kg | Dose | Kg | Dose |
|----|------|----|------|-----|------|-----|------|
| 40 | 5,2 | 63 | 8,2 | 86 | 11,2 | 109 | 14,2 |
| 41 | 5,3 | 64 | 8,3 | 87 | 11,3 | 110 | 14,3 |
| 42 | 5,5 | 65 | 8,5 | 88 | 11,4 | 111 | 14,4 |
| 43 | 5,6 | 66 | 8,6 | 89 | 11,6 | 112 | 14,6 |
| 44 | 5,7 | 67 | 8,7 | 90 | 11,7 | 113 | 14,7 |
| 45 | 5,9 | 68 | 8,8 | 91 | 11,8 | 114 | 14,8 |
| 46 | 6,0 | 69 | 9,0 | 92 | 12,0 | 115 | 15,0 |
| 47 | 6,1 | 70 | 9,1 | 93 | 12,1 | 116 | 15,1 |
| 48 | 6,2 | 71 | 9,2 | 94 | 12,2 | 117 | 15,2 |
| 49 | 6,4 | 72 | 9,4 | 95 | 12,4 | 118 | 15,3 |
| 50 | 6,5 | 73 | 9,5 | 96 | 12,5 | 119 | 15,5 |
| 51 | 6,6 | 74 | 9,6 | 97 | 12,6 | 120 | 15,6 |
| 52 | 6,8 | 75 | 9,8 | 98 | 12,7 | 121 | 15,7 |
| 53 | 6,9 | 76 | 9,9 | 99 | 12,9 | 122 | 15,9 |
| 54 | 7,0 | 77 | 10,0 | 100 | 13,0 | 123 | 16,0 |
| 55 | 7,2 | 78 | 10,1 | 101 | 13,1 | 124 | 16,1 |
| 56 | 7,3 | 79 | 10,3 | 102 | 13,3 | 125 | 16,3 |
| 57 | 7,4 | 80 | 10,4 | 103 | 13,4 | 126 | 16,4 |
| 58 | 7,5 | 81 | 10,5 | 104 | 13,5 | 127 | 16,5 |
| 59 | 7,7 | 82 | 10,7 | 105 | 13,7 | 128 | 16,6 |
| 60 | 7,8 | 83 | 10,8 | 106 | 13,8 | 129 | 16,8 |
| 61 | 7,9 | 84 | 10,9 | 107 | 13,9 | 130 | 16,9 |
| 62 | 8,1 | 85 | 11,1 | 108 | 14,0 | 131 | 17,0 |

Preparation:

1. Ensure there is a current valid prescription.
2. Make an infusion system and 100ml 0.9% Sodium Chloride.
3. Prepare the correct dose of Iron-Dextran Nanoparticles “(NANO contrast fluid “Combidex”) based on the dose table in this protocol and dissolve in 100ml 0.9% Sodium Chloride.
4. Review the dose and fluid calculations with a second practitioner.
5. Make sure the name and date of birth is specified on the NANO contrast fluid (Combidex).

Administration:

1. Put in the 18G intravenous cannula
2. Connect the 100ml 0.9% Sodium Chloride and start slow infusion
3. Call [name] (radiologist) to administer the NANO contrast fluid (Combidex)
4. The radiologist will change the 100ml 0.9% Sodium Chloride for the NANO contrast fluid (Combidex) and will specify date and time start infusion
5. The NANO contrast fluid (Combidex) will be administered in at least 30 minutes
6. At the time the NANO contrast fluid (Combidex) is completed, infusion will be changed to 0.9% Sodium Chloride will a slow rate.
7. Remove the intravenous cannula
8. The patient must remain at the health centre for at least 60 minutes after the end of infusion

Side effects:

Like every medical product, the NANO contrast fluid could have side effects. Side effects include headache, dizziness, light-headedness, nausea, an itchy skin. Normally, these side effects will resolve after a short period.

Allergic reaction:

Anaphylaxis is a severe, potentially fatal allergic reaction. It is characteristically unexpected and rapid in onset. If a patient has an anaphylaxis, the anaphylaxis protocol of St Vincent’s Hospital should be followed: appendix IV Contrast Allergy Protocol.

Should adverse reactions be noted at any time throughout the infusion:

1. **Stop the infusion immediately**
2. **Contact [name] (radiologist)**
3. **Refer to anaphylaxis protocol of St Vincent’s Hospital IV Contrast Allergy Protocol.**

IV CONTRAST ALLERGY PROTOCOL

5. Treatment of contrast reactions

Mild

Nausea / Vomiting

Supportive measures (antiemetics if prolonged vomiting)

Urticaria (mild)

Supportive measures

Urticaria (protracted)

Antihistamine (oral or intramuscular depending on severity)

Moderate

Marked Urticaria

- Antihistamines
- Consider use of Adrenaline 1:1000
 - In adults 0.1-0.25ml (0.1-0.25mg) intramuscularly – repeat as necessary
 - In children 0.01 mg/kg intramuscularly up to 0.3mg maximum dose

Bronchospasm

1. Oxygen by mask (6-10 l/min)
2. β -2-agonist (e.g. Salbutamol or Terbutaline) metered dose inhaler (2-3 deep inhalations).
In more severe cases, give Salbutamol or Terbutaline by nebuliser.
3. Consider Adrenaline
 - Normal blood pressure*
In adults: 1:1,000, 0.1-0.25 ml (0.1-0.25 mg) intramuscularly
[use smaller dose in patients with coronary artery disease or elderly patients]
In paediatric patients: 0.01 mg/kg up to 0.3 mg max intramuscularly
 - Decreased blood pressure*
In adults: 1:1,000, 0.5 ml (0.5 mg) intramuscularly
In paediatric patients: 0.01 mg/kg intramuscularly

Hypotension

- Isolated hypotension
 1. Elevate patient's legs
 2. Oxygen by mask (6-10 l/min)
 3. Intravenous fluid: rapidly, normal saline or lactated Ringer's solution
 4. If unresponsive: adrenaline: 1:1,000 , 0.5 ml (0.5 mg) intramuscularly, repeat as needed
- Vaso-vagal reaction (hypotension and bradycardia)
 1. Elevate patient's legs
 2. Oxygen by mask (6-10 l/min)
 3. Atropine
 - In adults 0.6-1.0 mg intravenously, repeat if necessary after 3-5 min, to 3 mg total (0.04 mg/kg).

- In paediatric patients give 0.02 mg/kg intravenously (max. 0.6 mg per dose) repeat if necessary to 2 mg total.
- 4. Intravenous fluids: rapid infusion of normal saline or Hartmann's solution 20 ml/kg, repeat as necessary.

Severe

Generalized anaphylactoid reaction

1. Stop contrast injection
2. Call for resuscitation team
3. Suction and maintain airway as needed
4. Oxygen by mask (6 – 10 l/min)
5. Intramuscular adrenaline, intramuscularly into the lateral thigh

In adults (and in children >25 kgs), Adrenaline 1:1,000

| | |
|---------|--------------------|
| < 50 kg | give 0.25 – 0.5 mL |
| > 50 kg | give 0.5 mL |

In children, Adrenaline 1:1,000

| | | |
|---------|-------|--------------|
| 1 year | 10 kg | give 0.1 mL |
| 3 years | 15 kg | give 0.15 mL |
| 5 years | 20 kg | give 0.2 mL |
| 8 years | 25 kg | give 0.25 mL |

- If necessary, repeat intramuscular dose every 5 minutes.
 - Large doses of adrenaline may be needed, up to a maximum of 5 mL (5 mg).
 - If the patient remains shocked after two intramuscular doses, consider an adrenaline infusion to restore blood pressure. (See notes 3,4).
6. Intravenous fluids (e.g. normal saline or Hartmann's solution 20mL/kg). Continue as necessary
 7. Ventilate patient if severe respiratory and circulatory collapse
 8. Additional measures:

| | |
|----------------------|---|
| Bronchodilators | For bronchospasm, give salbutamol or terbutaline by nebuliser, or aerosol with spacer device. |
| Corticosteroids | Hydrocortisone 2-6mg/kg or Dexamethasone 0.1-0.4 mg/kg intravenously |
| Nebulised adrenaline | May be tried for laryngeal oedema (5ml of 1:1,000) |

9. Supportive measures

Observe vital signs frequently, and, if possible, monitor ECG and pulse oximetry.

Arrange for transfer to hospital if reaction occurs in an outpatient facility.

Keep under observation for at least 4-6 hours after complete resolution of signs and symptoms, as biphasic reactions may occur.

Notes:

1. Adrenaline is life-saving and must be used promptly. Withholding adrenaline due to misplaced concerns of possible adverse effects can result in deterioration and death of the patient.
2. Adrenaline 1:1000 contains 1000 microgram in 1 mL (1 mg/mL). The volumes of adrenaline recommended for adults and children approximate to 5 to 10 microgram/kg. Children's weights are approximate for age.
3. If critical care facilities are not immediately available, give the following adrenaline infusion:
 - Mix 1 mg adrenaline (1 ampoule) in 1000 mL of normal saline
 - Start infusion at 5 mL/kg/hour (approx. 0.1 microgram/kg/minute)
 - Titrate rate up or down according to response.
4. Some cases are resistant to adrenaline, especially if the patient is taking beta blocking drugs. If adequate doses of adrenaline are not improving the situation, give glucagon 1 to 2 mg intravenously over 5 minutes.
5. Drug-assisted intubation for impending airway obstruction is a very high-risk procedure and should only be attempted by an expert.
6. Corticosteroids may modify the overall duration of a reaction and may prevent relapse. However, onset of action will be delayed. Never use these to the exclusion of adrenaline.

